**The study of stroke volume variation
combined with cardiac index in guiding volume
therapy in non-severe patients undergoing
intestinal neoplasm surgery**

NCT02841046

2019-8-10

The study of stroke volume variation combined with cardiac index in guiding volume therapy in non-severe patients undergoing intestinal neoplasm surgery

NCT02841046

【Abstract】 Objective To observe the application of goal-directed therapy (GDT) with the combination of stroke volume variation(SVV) and cardiac index(CI) as the primary judgment in non-severe patients undergoing intestinal neoplasm surgery. **Methods** 50 patients (ASA I - II,26-55 years old) scheduled for intestinal neoplasm surgery were divided randomly: group C using CI as the primary judgment for GDT and group S with the combination of SVV and CI. Patients in group C received a therapy with the goal of CI was no less than $2.5\text{L}\cdot\text{min}^{-1}\cdot\text{m}^{-2}$ while in group S was both SVV less than 12% and CI no less than $2.5\text{L}\cdot\text{min}^{-1}\cdot\text{m}^{-2}$. HR, MAP, CVP, CI, SVV were recorded 15 minutes after the induction of anesthesia(T1), making surgical incision(T2), performing intestinal anastomosis(T3) and closing the abdominal incision(T4). Oxygen delivery(DO₂),oxygen consumption(VO₂),O₂ extraction rate (ERO₂)and plasma Lactic acid(Lac) were monitored at T1 and T4. The volume of fluid, the incidence of adverse cardiovascular events, the exhaust time, hospital stay and complications were recorded. **Results** in group S, the amount of colloidal fluid increased and crystalline fluid decreased, the incidence of hypotension was lower than group C. DO₂, VO₂ were increased and Lac decreased at T4 in group S. The exhaust time and hospital stay were reduced in group S. (*P* <0.05) **Conclusions**

GDT with the combination of SVV and CI as the primary judgment maintained a more stable hemodynamic and better tissue perfusion, which helps to improve the prognosis of patients. This protocol was more suitable for the non-severe patients.

【Key words】 stroke volume variation; cardiac index; non-severe; volume therapy

Statistical Analysis methods : Spss19.0 statistical software was used to analyze the data ($\bar{x} \pm s$) means that independent sample t-test is used for normal distribution, independent sample rank sum test is used for non normal distribution, ANOVA is used for comparison of different time points of hemodynamics and oxygen metabolism indexes, paired t-test is used for comparison of two time points, chi square test is used for counting data, and $P < 0.05$ is statistically significant.

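### The group comparison of DO2, VO2, ERO2 and lactate makes no use of the T1 value already measured; if T1 precedes group-specific therapy, ANCOVA on T1 is a cheap gain in precision

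*Combined protocol and SAP*

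**What the plan says.** The Abstract (Methods) says that the 50 patients "scheduled for intestinal neoplasm surgery were divided randomly" to group C or group S, and that the oxygen measures and lactate "were monitored at T1 and T4". T1 is defined as "15 minutes after the induction of anesthesia(T1"). Neither the Abstract nor the statistical paragraph says whether group-specific therapy had started by then.

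The Statistical Analysis methods paragraph lists these methods for continuous data:

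- between groups: "independent sample t-test is used for normal distribution", and "independent sample rank sum test is used for non normal distribution";
- over time: "ANOVA is used for comparison of different time points of hemodynamics and oxygen metabolism indexes", and "paired t-test is used for comparison of two time points".

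It names no covariate, baseline adjustment or group-by-time term. In the Abstract (Results), DO2 and VO2 "were increased and Lac decreased at T4 in group S". The P value is given only as below 0.05, with no named comparator for this statement, no effect size and no confidence interval. No result is given for ERO2.

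**The concern.** Each patient has an early and a late value of all four measures, but the tests described for S against C look at the late value alone. When the early value is taken before the groups are treated differently, adjusting for it removes variation that has nothing to do with treatment. It also corrects the estimate for any chance difference between the groups at the start.

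The Abstract's conclusion that tissue perfusion was better in group S draws on these measures. Read as S–C differences, DO2, VO2 and lactate are already reported as significant, so the issue for them is not missed effects. It is how precise the differences are and how far they could reflect a T1 imbalance between two small groups. For ERO2, power could also improve.

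**Working it through.** The documents contain no sample-size or power calculation, so there is no stated figure to reproduce.

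**Inputs**

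- From the documents: 50 patients; significance level 0.05; measurements at T1 and T4.
- Assumed: 25 per arm (the split is not stated); two-sided testing; normal data; no dropout; within-arm T1–T4 correlation r of 0, 0.3, 0.5 or 0.7; true T4 difference d in SD units.
- The equal split matters little. The standard error of a group difference is √(1/25 + 1/25) = 0.283 SD, against √(1/20 + 1/30) = 0.289 SD for a 20:30 split.

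**Precision.** ANCOVA multiplies the variance of the T4 difference by 1 − r². This gives 1 − 0.09 = 0.91, 1 − 0.25 = 0.75 and 1 − 0.49 = 0.51 at r = 0.3, 0.5 and 0.7. ANCOVA also pays a small price for estimating the slope. The table comes from simulation with the covariate fitted, 100,000 trials per setting:

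| | Unadjusted | ANCOVA r = 0 | r = 0.3 | r = 0.5 | r = 0.7 |
|---|---|---|---|---|---|
| Mean 95% CI half-width (SD) | 0.566 | 0.572 | 0.546 | 0.495 | 0.408 |
| Power, d = 0.4 | 28.5% | 27.9% | 30.1% | 35.6% | 48.5% |
| Power, d = 0.6 | 54.8% | 53.9% | 57.8% | 66.2% | 82.1% |
| Power, d = 0.8 | 79.2% | 78.1% | 82.1% | 88.6% | 97.0% |
| Power, d = 1.0 | 93.3% | 92.8% | 94.9% | 97.6% | 99.8% |

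With no true effect, both tests reject in 5.0% of trials at every r. A noncentral t calculation at d = 0.8 agrees: 79% unadjusted, and 82%, 89% and 97% with ANCOVA at r = 0.3, 0.5 and 0.7.

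**Chance imbalance at T1.** The T1 difference has standard error 0.283 SD. It therefore exceeds 0.3 SD in 29% of trials (0.3/0.283 = 1.06 standard errors) and 0.5 SD in 8% (0.5/0.283 = 1.77 standard errors). With no true effect, a T1 difference D shifts the expected unadjusted T4 difference by r × D:

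| | r = 0.3 | r = 0.5 | r = 0.7 |
|---|---|---|---|
| Shift at D = 0.5 SD | 0.15 SD | 0.25 SD | 0.35 SD |
| Unadjusted false-positive rate at D = 0.5 | 7.0% | 10.5% | 15.2% |
| ANCOVA false-positive rate at D = 0.5 | 5.0% | 4.9% | 5.0% |
| Shift at D = 0.3 SD | 0.09 SD | 0.15 SD | 0.21 SD |
| Unadjusted false-positive rate at D = 0.3 | 5.1% | 5.1% | 4.6% |
| ANCOVA false-positive rate at D = 0.3 | 5.0% | 5.0% | 5.1% |

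At 0.3 SD, then, only the estimate moves. With no imbalance the unadjusted rate is below 5% (2.4% at r = 0.5), which is why it averages 5% over all trials.

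**If T1 follows the start of therapy.** Suppose, as an assumption, that therapy has already moved T1 by 0.3 SD and the true T4 effect is 0.8 SD. ANCOVA then estimates 0.8 − r × 0.3, which is 0.71, 0.65 or 0.59 SD at r = 0.3, 0.5 or 0.7. Power falls from 79% to about 71–72% at r = 0.3 and 0.5. Adjustment in that case removes part of the effect.

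**The case against.** The strongest reply is that nothing here is wrong. The unadjusted test is valid under randomisation, and preferring ANCOVA is a matter of efficiency. That is correct, and it is why the point is minor.

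Second, the form of the ANOVA is not stated. A repeated-measures model with a group term would bring T1 into an S–C contrast, and a purely within-arm ANOVA on two time points would duplicate the paired t-test. This cannot be excluded, but the text describes the ANOVA as a comparison of time points and names no group term.

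Third, the benefit depends on facts the documents do not give: the correlation, the arm sizes, any actual T1 imbalance and, above all, the timing of T1. All of this stands. The timing question is why the change must be conditional, because adjusting for a T1 taken after therapy began would do harm.

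Fourth, the missing comparator may matter more to the perfusion claim than the choice of test, because the T4 statement could describe a change from T1 within group S. This is fair. If so, the reported P values do not settle the S–C question for any of the four measures.

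Finally, the simulations cover normal data only. The log scale proposed for outcomes analysed by rank sum is itself a post hoc choice and may not cure non-normality.

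**Conclusion.** The concern holds as a minor one, with medium confidence. As described, the S–C comparison of DO2, VO2, ERO2 and lactate leaves out the T1 value. With 25 per arm assumed, the gain from using it is slight at a correlation of 0.3, moderate at 0.5 and large at 0.7; if T1 is uninformative, the loss is about one point of power or less. The protection against imbalance matters chiefly in the roughly 8% of trials with a T1 difference above 0.5 SD. All of this requires that T1 precede group-specific therapy, which the documents leave open.

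**What to change.** 1. State whether T1 was recorded before group-specific therapy began.
2. If it was, analyse each of the four measures by ANCOVA of the T4 value on group and T1. Report the adjusted S–C difference with its 95% CI beside the unadjusted result, labelled post hoc because results already exist. Use the raw scale where the t-test was used and the log scale where the rank sum test was used, so that the scale follows a choice already made.
3. If it was not, keep the unadjusted comparison at T4 and add its 95% CI.
4. In either case, restate the T4 result with its comparator (versus group C, if that is what was tested), and do not offer within-arm paired P values as evidence of a difference between groups.

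The cost is one sentence in the statistical methods and one SPSS re-run, with no new data. The adjusted result can serve only as a sensitivity analysis, and at a correlation of 0.3 it will add little.

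### With about 25 patients per arm, does leaving the version of the chi-square test unstated undermine the count outcomes?

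*Combined protocol and SAP*

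**What the plan says.** The Statistical Analysis methods paragraph covers every binary outcome in one clause: "chi square test is used for counting data". The significance threshold is 0.05 and the software is SPSS 19.0. The paragraph does not mention a continuity correction, a minimum expected count or an exact test.

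The Abstract supplies the rest. Under Methods, "50 patients (ASA I - II,26-55 years old) scheduled for intestinal neoplasm surgery were divided randomly" into groups C and S. No allocation ratio is stated. Among the data collected, "the incidence of adverse cardiovascular events, the exhaust time, hospital stay and complications were recorded", so the count outcomes are adverse cardiovascular events and complications. Under Results, one count outcome is reported as different: in group S "the incidence of hypotension was lower than group C". No numerator, rate or exact P-value is attached to it. A single P<0.05 label closes that group of results.

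**The concern.** With about 25 patients per arm, a 2x2 table takes few values, and the continuity correction moves the P-value a long way. The uncorrected (Pearson) and corrected (Yates) statistics could both be called a chi-square test, yet they can fall on opposite sides of 0.05. Pearson is always the more permissive of the two. A version chosen after seeing the data could therefore only move a result towards significance relative to the corrected test.

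The usual advice to switch to an exact test when an expected count is below 5 would not settle the matter, because many of the disagreements arise in tables that are not sparse. What seems to be at stake is the lower incidence of hypotension in group S, which bears on the conclusion that haemodynamics were more stable. From the documents a reader cannot tell which version was used or how close to 0.05 the result lies.

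**Working it through.** **Inputs.** From the documents: 50 patients, two groups, a chi-square test, threshold 0.05. Assumed: 25 per arm (24:26 as a sensitivity case), two-sided testing, and all event rates. The plan gives no power, event rate or effect size, so it has no figure of its own to reproduce.

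**Formulas.** Let *a* and *b* be the patients with an event among *n* and *m*, with N = n + m and t = a + b.

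- Difference term: d = |a(m − b) − b(n − a)|
- Pearson: X² = N·d² / [n·m·t·(N − t)]
- Yates: the same, with d replaced by d − N/2

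**Two tables at 25:25.**

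- *4 vs 0 (sparse).* d = |4×25 − 0×21| = 100. Pearson: 50×100²/(25×25×4×46) = 500,000/115,000 = 4.35, P = 0.037. Yates: d = 75, X² = 281,250/115,000 = 2.45, P = 0.118. Fisher: P = 0.110.
- *11 vs 4 (smallest expected count 7.5).* d = |11×21 − 4×14| = 175. Pearson: 50×175²/(25×25×15×35) = 1,531,250/328,125 = 4.67, P = 0.031. Yates: d = 150, X² = 1,125,000/328,125 = 3.43, P = 0.064. Fisher: P = 0.062.

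The disagreement is therefore real.

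**All tables.** At 25:25 there are 26×26 = 676 tables. Pearson is significant in 408 and Yates in 358. They disagree in 50, always with Pearson significant and Yates not. In 34 of the 50, every expected count is at least 5. The proportion 50/408 = 12% weights all tables equally, so it is not the probability of anything.

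**Is the natural reading sound?** Weighting the tables by two independent binomials with a common rate gives the true type I error:

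| Common rate | Pearson | Yates | Verdicts differ |
|---|---|---|---|
| 10% | 4.9% | 0.6% | 4.3% |
| 20% | 5.5% | 1.7% | 3.8% |
| 30% | 5.4% | 2.2% | 3.1% |
| 50% | 6.5% | 3.3% | 3.2% |

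Pearson stays close to the nominal 5%, with a mild excess at high rates. Yates is conservative throughout.

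**How often would the version decide the verdict if the arms truly differ?**

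| Assumed true rates | Power, Pearson | Power, Yates | Verdicts differ |
|---|---|---|---|
| 20% vs 0% | 77% | 38% | 38% |
| 20% vs 2% | 59% | 27% | 32% |
| 30% vs 5% | 71% | 49% | 22% |
| 40% vs 15% | 53% | 38% | 16% |
| 50% vs 20% | 64% | 51% | 13% |
| 50% vs 10% | 91% | 83% | 8% |
| 60% vs 20% | 87% | 79% | 8% |
| 60% vs 10% | 98% | 96% | 2% |

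The high values occur where Pearson power is middling and P-values cluster near 0.05. They fall quickly once the difference is large.

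**Sensitivity to the split.** At 24:26, Pearson's type I error is 4.5% to 6.5% for the same common rates. For 20% vs 2% the verdicts differ with probability 18% or 27%, depending on which arm is larger. For 50% vs 20% it is 12% or 14%. The conclusion does not hinge on an exact 25:25 split.

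**The case for a change.** The strongest counter-argument conditions on what has been reported. Hypotension is presented as lower under a P<0.05 label, so the relevant question is how many Pearson-significant results would fail with the correction. That share is the probability of differing verdicts divided by Pearson power: 0.321/0.589 = 54% for 20% vs 2%, 0.128/0.638 = 20% for 50% vs 20%, and 0.023/0.982 = 2% for 60% vs 10%. With no true difference it is higher still, for example 0.043/0.049 = 88% at a 10% common rate. One sentence and the counts for each arm would remove the doubt.

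Two parts of this stand. The omission is real, and naming the software does not fill it. A borderline table could also change its verdict.

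The rest does not carry. Failing the corrected test is evidence against a result only if the corrected test is the better yardstick. Its true size of 0.6% to 3.3% against a nominal 5% shows that it is not. Fisher is similar where the question matters most, with power of 30% at 20% vs 2%. A continuity correction is a modification that one expects to see named, so its absence points to Pearson. The documents give no hypotension counts, so the shares above describe assumed rates and say nothing about this trial's table. The counts may be missing simply because the text is an abstract. It might also be asked whether patients or events are counted, but an outcome described as an incidence reads naturally as patients affected.

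**Conclusion.** The concern does not call for a change. The plan leaves out a detail, and the ordinary reading of its words supplies a sound test: uncorrected Pearson chi-square, with true type I error of 4.9% to 6.5% at common rates of 10% to 50%. No better test is being passed over. The correction would roughly halve power at 20% vs 2% (59% to 27%) and would make the test conservative without protecting against any material excess of false positives.

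The version decides the verdict in about 2% to 38% of trials across the assumed true differences, and in 3% to 4% when there is none. That range is too dependent on assumption to support a claim about the reported hypotension result, on which the effect is unknown. Only the count outcomes are touched; the haemodynamic, oxygen-metabolism, fluid-volume, exhaust-time and hospital-stay comparisons use other tests. These conclusions rest on about 25 patients per arm, two-sided testing at 0.05, independent binomial arms and patients as the unit.
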